### **8.3 Study procedures**

An extra blood sample (1 EDTA tube) is obtained in the week preoperative by venipuncture. From this blood sample, hemoglobin tests are performed in the hospital's laboratory. Postoperative hemoglobin value will be obtained from the blood sample that is performed in all bariatric patients on the first postoperative day. Information on peroperative use of hemostatic staples, administration of packed cells, postoperative tranexamic acid, rates of postoperative hemorrhage and VTE are obtained from the electronic patient file. Routine venous duplex ultrasound will not be performed. Therefore, only clinically significant VTEs are registered.

### **8.4 Withdrawal of individual subjects**

Subjects can leave the study at any time for any reason if they wish to do so without any consequences. The investigator can decide to withdraw a subject from the study for urgent medical reasons, for example such as mentioned in the exclusion criteria.

#### **8.4.1 Specific criteria for withdrawal (if applicable)**

Not applicable.

### **8.5 Replacement of individual subjects after withdrawal**

After withdrawal, individual subjects will be replaced by including new patients at the outpatient clinic to guarantee the needed number for sufficient power for analysis.

### **8.6 Follow-up of subjects withdrawn from treatment**

All subjects withdrawn from treatment, will be followed-up according to the bariatric surgery guidelines.

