#### **4.3 Exclusion criteria**

A potential subject who meets any of the following criteria will be excluded from participation in this study: Patients unwilling to give informed consent, patients with a medical history of bleeding or VTE and patients who use therapeutic anticoagulants. Patients will also be excluded in case of peroperative arterial bleeding or (iatrogenic) bleeding coming from surrounding organs or vascular structures such as the liver or the spleen.

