#### **8.1.2 Secondary study parameters/endpoints (if applicable)**

Secondary outcome measures are the decrease in hemoglobin after the procedure at 1 day postoperative, rates of postoperative hemorrhage (i.e. hemorrhage needing administration of packed cells or a surgical or radiological re-intervention) within 30 days postoperative and rates of VTE within 3 months postoperative.

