### 9.2.2 Serious adverse events (SAEs)

A serious adverse event is any untoward medical occurrence or effect that

- results in death;
- is life threatening (at the time of the event);
- requires hospitalisation or prolongation of existing inpatients' hospitalisation;
- results in persistent or significant disability or incapacity;
- is a congenital anomaly or birth defect; or
- any other important medical event that did not result in any of the outcomes listed above due to medical or surgical intervention but could have been based upon appropriate judgement by the investigator.

An elective hospital admission will not be considered as a serious adverse event.

The investigator will report all SAEs that occur within 3 months postoperative to the sponsor without undue delay after obtaining knowledge of the events.

The sponsor will report the SAEs through the web portal *ToetsingOnline* to the accredited METC that approved the protocol, within 7 days of first knowledge for SAEs that result in death or are life threatening followed by a period of maximum of 8 days to complete the initial preliminary report. All other SAEs will be reported within a period of maximum 15 days after the sponsor has first knowledge of the serious adverse events.

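### Patients who have had the infusion can be withdrawn or excluded and then replaced, and nothing keeps their 30-day haemorrhage and 3-month VTE outcomes in the comparison

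*Protocol*

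**What the plan says.** **Timing.** Patients are randomised after consent at the outpatient clinic (Protocol 8.2). They receive a single infusion at induction (3, 5.1), given over 15 to 30 minutes (6.6).

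**Grounds for removal.** Section 4.3 lists "patients with a medical history of bleeding or VTE and patients who use therapeutic anticoagulants", and then adds a ground that arises only during surgery: "Patients will also be excluded in case of peroperative arterial bleeding or (iatrogenic) bleeding coming from surrounding organs". Section 8.4 states: "The investigator can decide to withdraw a subject from the study for urgent medical reasons, for example such as mentioned in the exclusion criteria". Section 8.4.1, on specific withdrawal criteria, reads "Not applicable".

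**Replacement.** Section 8.5: "After withdrawal, individual subjects will be replaced by including new patients at the outpatient clinic". The stated purpose is to secure enough patients for a sufficiently powered analysis.

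**Follow-up afterwards.** Section 8.6 has one sentence: "All subjects withdrawn from treatment, will be followed-up according to the bariatric surgery guidelines".

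**Outcomes at issue.** Section 8.1.2 sets the windows for postoperative haemorrhage and thromboembolism: "within 30 days postoperative and rates of VTE within 3 months postoperative". Section 8.3 takes both from the electronic patient file, without routine duplex screening. Section 9.2.2 adds: "The investigator will report all SAEs that occur within 3 months postoperative to the sponsor".

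**The concern.** Once the infusion has been given, no study treatment is left to stop. Withdrawal from the study after that point can affect only participation and data. Two of the grounds available are related to the safety outcomes. Bleeding during surgery is one. New therapeutic anticoagulation, which a patient treated for a VTE would be taking, is possibly the other. The replacement rule then suggests that the withdrawn patient no longer counts in the analysed number.

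At stake are the comparison of postoperative haemorrhage and the trial's main harm question, whether tranexamic acid increases VTE. If treated patients leave that comparison for reasons related to bleeding or its treatment, the remaining arms are no longer the randomised ones and the event counts may be incomplete. With counts this small, one patient matters to what is reported.

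**Working it through.** **1. The plan's own calculated figure.** Section 4.4 gives 2 × 36 = 72. With a control rate of 63.3% (section 1), halved to 31.65%, two-sided alpha 5%, power 80% and the unpooled normal formula:

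n per arm = (1.960 + 0.842)² × [0.633 × 0.367 + 0.3165 × 0.6835] / 0.3165² = 35.2, rounded up to 36, so 72 in total.

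The figure reproduces. It concerns the clip endpoint and is not affected by this point.

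**2. Which removal grounds can arise after the infusion?**

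| Ground (4.3, used as an example in 8.4) | Can it arise after the infusion? |
|---|---|
| Bleeding during surgery, arterial or from surrounding organs | Yes. It comes after randomisation and normally after the infusion has started |
| Use of therapeutic anticoagulants | Possibly. It is a current state that could become true later |
| Medical history of bleeding or VTE | Not on its wording. It is an eligibility condition |

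**3. What happens to such a patient?** Section 8.4 allows removal from the study, and 8.5 brings in a replacement. Section 8.6 speaks of withdrawal from treatment, which hardly fits a single dose already given, and it names guideline care only. No sentence says that the patient's 30-day and 3-month outcomes are still extracted, or that the patient stays in the assigned arm.

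**4. How many events are expected?** Inputs are the centre's rates in section 1 (haemorrhage after sleeve gastrectomy 2.2%, VTE 0.05%), with N = 100 (section 3) or 72 (section 4.4). Expected events = N × rate, and P(at least one) = 1 − (1 − rate)^N.

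| | N = 72 | N = 100 |
|---|---|---|
| Haemorrhages expected | 72 × 0.022 = 1.6 | 100 × 0.022 = 2.2 |
| P(at least one haemorrhage) | 0.80 | 0.89 |
| VTEs expected | 72 × 0.0005 = 0.036 | 100 × 0.0005 = 0.05 |
| P(at least one VTE) | 3.5% | 1 − 0.9995^100 = 4.9% |

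**5. What does one lost patient change?** One haemorrhage is 1/2.2, about 45% of the number expected in 100 patients. For VTE with 50 patients on tranexamic acid, the exact (Clopper-Pearson) 95% upper limit is 10.6% for 1/50. If that patient is removed and replaced by one without an event, 0/50 gives 1 − 0.025^(1/50) = 7.1%.

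**6. Does the reason for withdrawal matter?** The documents give no withdrawal rate, so I assume 2%, 5% and 10% of 100 patients. If withdrawal is unrelated to outcome, the expected loss of haemorrhages is 2 × 0.022 = 0.04, 5 × 0.022 = 0.11 and 10 × 0.022 = 0.22. These are negligible, so the concern rests on withdrawal that is related to outcome.

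**7. Does a test result depend on it?** Fisher's exact test with 50 per arm gives p = 1.00 for 1 versus 0, 0.49 for 2 versus 0, 0.056 for 5 versus 0 and 0.027 for 6 versus 0. At the expected counts no test reaches 5%, with or without the lost patient.

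**The case against.** A reader might infer several stronger things, and the documents do not support them.

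- **That withdrawn patients leave study follow-up.** Section 8.6 does not say so. Under 8.3, routine care plus the patient file is how haemorrhage and VTE are found in every patient, so guideline follow-up is not a lesser route. An event is lost only if extraction stops or the patient is left out of the analysis, and no sentence orders either. A patient withdrawn after an embolism or a qualifying bleed has already had the event on record.
- **That the withdrawal grounds mirror the endpoints.** For bleeding and VTE, 4.3 speaks of medical history, not of a new postoperative event. Section 8.4 cites the criteria only as a discretionary example.
- **That 8.6 contradicts the SAE duty.** Section 9.2.2 makes no exception for withdrawn patients. It is a partial safeguard and would catch most re-interventions and clinical VTEs.
- **That 8.4 and 8.4.1 contradict each other.** Discretionary withdrawal with an example is compatible with having no specific criteria.

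All four corrections stand. It can also be said that the analysis of withdrawn patients is commonly left to the SAP, which is not at hand, and that limits of 7.1% and 10.6% are both uninformative against a rate of 0.05%. Both remarks are fair, but they do not dispose of the point. Removal after treatment and replacement are rules stated in the protocol itself, and an SAP cannot analyse outcomes that were not collected. Reporting an SAE to the sponsor and the ethics committee does not by itself place the patient in the comparisons of section 10. Because source data verification is not performed (12.2), an omission is also less likely to be noticed.

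**Conclusion.** The point holds in limited form. Read together, sections 4.3, 8.4 and 8.5 allow a patient who has already received the infusion to be removed and replaced. The case is clear for bleeding during surgery and possible for new anticoagulant use. Section 8.6 does not secure that patient's 30-day and 3-month outcomes for the comparison.

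The effect is on the reported safety counts: about 2.2 haemorrhages and 0.05 VTEs are expected in 100 patients, so one lost patient can alter them visibly. No powered test changes, and the sample size is untouched. This rests on the centre's historical rates applying to the trial, on 50 patients per arm, and on withdrawal being related to outcome. How often that would happen cannot be judged from the protocol. The change is worth making because it protects the trial's main harm comparison at almost no cost.

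**What to change.** In sections 8.4 to 8.6, and consistently with the exclusion for bleeding during surgery in 4.3, state that:

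1. Every randomised patient who received any study infusion stays in the collection of 30-day haemorrhage, 3-month VTE and SAEs from the electronic patient file, and is analysed for these outcomes in the assigned arm, unless the patient withdraws consent for data use.
2. Decisions about a patient's care do not by themselves end data collection.
3. A replacement patient is added to these analyses and does not take the place of a treated patient.

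Investigator discretion over care need not be touched. The cost is protocol wording and one line in the patient information on continued record review. No visit or test is added, because the data already come from the patient file.

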### **8.7 Premature termination of the study**

In case of substantially more (serious) adverse events in one of each groups that are correlated to tranexamic acid, the study can be terminated prematurely in consultation with the METC.

## **9. SAFETY REPORTING**

### **9.1 Temporary halt for reasons of subject safety**

In accordance to section 10, subsection 4, of the WMO, the sponsor will suspend the study if there is sufficient ground that continuation of the study will jeopardise subject health or safety. The sponsor will notify the accredited METC without undue delay of a

temporary halt including the reason for such an action. The study will be suspended pending a further positive decision by the accredited METC. The investigator will take care that all subjects are kept informed.

## 9.2 AEs, SAEs and SUSARs

### 9.2.1 Adverse events (AEs)

Adverse events are defined as any undesirable experience occurring to a subject during the study, whether or not considered related to the experimental intervention. All adverse events reported spontaneously by the subject or observed by the investigator or his staff will be recorded.

### 9.2.2 Serious adverse events (SAEs)

A serious adverse event is any untoward medical occurrence or effect that

- results in death;
- is life threatening (at the time of the event);
- requires hospitalisation or prolongation of existing inpatients' hospitalisation;
- results in persistent or significant disability or incapacity;
- is a congenital anomaly or birth defect; or
- any other important medical event that did not result in any of the outcomes listed above due to medical or surgical intervention but could have been based upon appropriate judgement by the investigator.

An elective hospital admission will not be considered as a serious adverse event.

The investigator will report all SAEs that occur within 3 months postoperative to the sponsor without undue delay after obtaining knowledge of the events.

The sponsor will report the SAEs through the web portal *ToetsingOnline* to the accredited METC that approved the protocol, within 7 days of first knowledge for SAEs that result in death or are life threatening followed by a period of maximum of 8 days to complete the initial preliminary report. All other SAEs will be reported within a period of maximum 15 days after the sponsor has first knowledge of the serious adverse events.

### 9.2.3 Suspected unexpected serious adverse reactions (SUSARs)

Adverse reactions are all untoward and unintended responses to an investigational product related to any dose administered.

Unexpected adverse reactions are SUSARs if the following three conditions are met:

1. the event must be serious (see chapter 9.2.2);
2. there must be a certain degree of probability that the event is a harmful and an undesirable reaction to the medicinal product under investigation, regardless of the administered dose;
3. the adverse reaction must be unexpected, that is to say, the nature and severity of the adverse reaction are not in agreement with the product information as recorded in:
  - Summary of Product Characteristics (SPC) for an authorised medicinal product;
  - Investigator's Brochure for an unauthorised medicinal product.

The sponsor will report expedited the following SUSARs through the web portal *ToetsingOnline* to the METC:

- SUSARs that have arisen in the clinical trial that was assessed by the METC;
- SUSARs that have arisen in other clinical trials of the same sponsor and with the same medicinal product, and that could have consequences for the safety of the subjects involved in the clinical trial that was assessed by the METC.

The remaining SUSARs are recorded in an overview list (line-listing) that will be submitted once every half year to the METC. This line-listing provides an overview of all SUSARs from the study medicine, accompanied by a brief report highlighting the main points of concern.

The expedited reporting of SUSARs through the web portal Eudravigilance or *ToetsingOnline* is sufficient as notification to the competent authority.

The sponsor will report expedited all SUSARs to the competent authorities in other Member States, according to the requirements of the Member States.

The expedited reporting will occur not later than 15 days after the sponsor has first knowledge of the adverse reactions. For fatal or life threatening cases the term will be maximal 7 days for a preliminary report with another 8 days for completion of the report.

### 9.3 Annual safety report

In addition to the expedited reporting of SUSARs, the sponsor will submit, once a year throughout the clinical trial, a safety report to the accredited METC, competent authority, and competent authorities of the concerned Member States.

This safety report consists of:

- a list of all suspected (unexpected or expected) serious adverse reactions, along with an aggregated summary table of all reported serious adverse reactions, ordered by organ system, per study;
- a report concerning the safety of the subjects, consisting of a complete safety analysis and an evaluation of the balance between the efficacy and the harmfulness of the medicine under investigation.

### 9.4 Follow-up of adverse events

All AEs will be followed until they have abated, or until a stable situation has been reached. Depending on the event, follow up may require additional tests or medical procedures as indicated, and/or referral to the general physician or a medical specialist. SAEs need to be reported till end of study within the Netherlands, as defined in the protocol

### 9.5 Data Safety Monitoring Board (DSMB) / Safety Committee

Not applicable.

## 10. STATISTICAL ANALYSIS

Statistical analyses will be performed using IBM-SPSS version 24 (IBM Corporation, Armonk, New York, USA). Efforts will be made to prevent missing data by checking completeness of collected data. Missing data may be expected because of failed hemoglobin tests, or due to (less likely) unregistered administration of tranexamic acid or packed cells.

### 10.1 Primary study parameter(s)

Differences in use of hemostatic staples (yes/no) between the 2 groups will be determined using Chi-Square tests. The difference in hemoglobin decrease will be tested using multivariate linear regression analysis, correcting for comorbidities (hypertension, diabetes, dyslipidemia) and use of hemostatic staples. These same analyses will be performed to assess the differences in amount of patients needing to undergo a re-

intervention, but adding administration of postoperative tranexamic acid as a covariate. Results will be evaluated at a significance threshold of  $p < 0.05$  (two-sided).

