## SUMMARY

**Rationale:** Fast-track protocols are frequently used in bariatric surgery and often include short-term thromboprophylaxis and short length of hospital stay. These treatment strategies may negatively affect the occurrence and diagnosis of postoperative hemorrhage. Over the years, the rates of venous thromboembolic events (VTE) decrease, while there seems to be an increase in the occurrence of postoperative hemorrhage. Tranexamic acid (TA) is a plasminogen inhibitor which inhibits fibrinolysis. Peroperative administration of TA may lower the incidence of postoperative hemorrhage.

**Objective:** This trial aims to investigate if peroperative administration of TA can reduce the peroperative and postoperative hemorrhage rates in laparoscopic sleeve gastrectomy.

**Study design:** This is a double-blind, single center randomized controlled trial.

**Study population:** Patients eligible for bariatric surgery according to the IFSO guidelines and undergoing a laparoscopic sleeve gastrectomy. Patients unwilling to give informed consent, patients with a medical history of bleeding or VTE and patients that use therapeutic anticoagulants will be excluded.

**Intervention (if applicable):** Patients are randomized between 2 groups: 1) Single dose of 1500 mg TA to be administered during induction of the procedure by anesthesiologist, and 2) Standard protocol with administration of placebo infusion.

**Main study parameters/endpoints:** Primary outcome measure is peroperative use of hemostatic clips. Secondary outcome measures are the decrease in hemoglobin after the procedure, rates of postoperative hemorrhage (i.e. hemorrhage needing administration of packed cells or a surgical or radiological re-intervention) and rates of VTE.

**Nature and extent of the burden and risks associated with participation, benefit and group relatedness:** All patients will be required to undergo one additional blood drawing in the week prior to the procedure which will be performed at their weighing appointment, meaning that this will not require an extra hospital visit. TA has very little side effects. Therefore we conclude that the expected benefits of the intervention outweigh the minor risks involved.

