#### **4.4 Sample size calculation**

The performed power analysis (power= 80%, alfa=5% two-sided) calculated a required sample size of  $2 \times 36 = 72$  patients. The analysis was based on an expected 50% decrease of the percentage of patients for whom placement of hemostatic staples was required peroperatively.

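### The hemoglobin-decrease regression leaves out preoperative hemoglobin, which the trial already measures, so it gives up some precision and corrects chance baseline imbalance with a fixed, probably wrong slope

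*Protocol*

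**What the plan says.** Section 8.1.2 names the endpoint: "Secondary outcome measures are the decrease in hemoglobin after the procedure at 1 day postoperative". Section 10.1 gives the analysis: "The difference in hemoglobin decrease will be tested using multivariate linear regression analysis", "correcting for comorbidities (hypertension, diabetes, dyslipidemia) and use of hemostatic staples". No other section adds a covariate to this model. Section 8.1.3 says only that comorbidities are taken into account and that blood pressure and duration of surgery are recorded.

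Both hemoglobin values are planned. For the first, section 8.3 states: "An extra blood sample (1 EDTA tube) is obtained in the week preoperative by venipuncture". Its purpose is explicit: "From this blood sample, hemoglobin tests are performed in the hospital's laboratory". The Summary presents this draw as the burden that participation places on all patients: "one additional blood drawing in the week prior to the procedure which will be performed at their weighing appointment". The second value comes from routine care: "Postoperative hemoglobin value will be obtained from the blood sample that is performed in all bariatric patients on the first postoperative day".

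**The concern.** The protocol chooses an adjusted regression and writes out the adjustment variables, but the list lacks the baseline value of the outcome itself. A change score assumes that each extra unit of preoperative hemoglobin carries over in full to day 1. When the pre-post correlation is below 1 and the two standard deviations are similar, the true slope is below 1. Patients who start higher then tend to fall more, whatever the treatment.

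There are two consequences. Residual variance is larger than it need be. And if one arm happens to start higher, part of that difference appears as a difference in hemoglobin decrease. A higher start in the tranexamic acid arm would hide some benefit, and a lower start would exaggerate it.

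This endpoint deserves a good analysis because it is the only continuous secondary outcome. The others are rare: section 1 gives a local postoperative hemorrhage rate of 2.2% after sleeve gastrectomy, about 50 × 0.022 = 1.1 events in an arm of 50, and a VTE rate of 0.05%.

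**Working it through.** **The plan's own figure.** The protocol states no power, standard deviation or correlation for hemoglobin. Its only sample-size figure, 2 × 36 = 72 (section 4.4, "power= 80%, alfa=5% two-sided"), concerns the primary endpoint. Taking the 63.3% from section 1 as the control rate and halving it to 31.65%, the unpooled two-proportion formula gives (1.96 + 0.84)² × (0.633 × 0.367 + 0.3165 × 0.6835) / 0.3165² = 35.15, so 36 per arm. The figure reproduces and has no bearing on this point.

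**Inputs.**
- 100 patients, equal allocation, so 50 per arm (section 3).
- Outcome: the decrease, preoperative minus day 1 (sections 8.1.2 and 8.3).
- Assumed, because the protocol is silent: equal standard deviations before and after surgery (set to 1), and ρ from 0.5 to 0.9.
- Simplification: the other covariates in the planned model are ignored.

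**Precision.** The variance of the decrease is 1 + 1 − 2ρ = 2(1 − ρ). With baseline in the model, the residual variance is 1 − ρ². The ratio is (1 − ρ²) / [2(1 − ρ)] = (1 + ρ)/2. The standard error of the treatment difference is √(residual variance × 2/50). The last column is 100 divided by the ratio.

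| ρ | Variance, decrease alone | Variance, baseline added | Ratio | SE alone | SE with baseline | CI narrower by | 100 patients worth |
|---|---|---|---|---|---|---|---|
| 0.5 | 1.00 | 0.75 | 0.75 | 0.200 | 0.173 | 13% | 133 |
| 0.7 | 0.60 | 0.51 | 0.85 | 0.155 | 0.143 | 8% | 118 |
| 0.9 | 0.20 | 0.19 | 0.95 | 0.089 | 0.087 | 2.5% | 105 |

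**Baseline imbalance.** With 50 per arm, the chance difference in mean baseline has standard error √(2/50) = 0.20 SD. The decrease retains (1 − ρ) of it. A one-standard-error imbalance therefore moves the estimate by:
- ρ = 0.5: 0.5 × 0.20 = 0.10 SD, which is 0.10/0.200 = 0.50 of the estimate's own SE
- ρ = 0.7: 0.3 × 0.20 = 0.06 SD, or 0.06/0.155 = 0.39 SE
- ρ = 0.9: 0.1 × 0.20 = 0.02 SD, or 0.02/0.089 = 0.22 SE

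**Simulation check.** In 8,000 simulated trials of 50 per arm at each of ρ = 0.6, 0.8 and 0.9, the variance ratio of the treatment estimate was 0.80, 0.91 and 0.96, against 0.80, 0.90 and 0.95 from the formula. The small excess is what estimating the slope and simulation error would produce. The change-score estimate moved by 0.40, 0.20 and 0.10 per unit of imbalance. The adjusted estimate moved by about 0.

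**Choice of outcome.** Because the decrease is baseline minus day 1, a model containing baseline gives the same treatment coefficient for either outcome, apart from sign. Only the baseline coefficient changes.

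**The case against.** A change-score regression is a conventional and valid analysis. Randomization keeps its estimate unbiased on average, the type I error rate holds, and the variation caused by baseline imbalance is already inside the planned confidence interval. All of that stands. So a reader who infers that imbalance goes uncorrected, or that the result is biased as such, goes too far. Baseline is subtracted in full, and what remains is the fraction (1 − ρ), an error only conditional on the imbalance that happens to occur.

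The size of the gain rests on an assumed ρ and on equal standard deviations. This also stands. At ρ = 0.9 the gain is slight, and if the day-1 values are enough more variable than the preoperative ones that the true slope is 1, there is none. The comparison also leaves out the comorbidities and staple use that the planned model contains, so it is not an exact figure for that model.

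Section 10.1 does not call its covariate list exhaustive, and a statistical analysis plan not seen here might add baseline. That would settle the point. As written, though, the protocol names its covariates and this one is not there.

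Three further inferences lack support:
- **Complete measurement.** Section 10 expects some failed hemoglobin tests, so the endpoint is planned in everyone rather than certain to be measured in everyone.
- **Strongest predictor of the fall.** Nothing in the protocol says this of baseline. Under the assumptions above, its correlation with the fall is √((1 − ρ)/2), only 0.22 at ρ = 0.9.
- **Body weight as a needed covariate.** The protocol gives no evidence that weight predicts the fall, and section 8.1.3 does not list weight among the recorded variables.

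**Conclusion.** The point holds as an efficiency weakness in a secondary analysis. Section 10.1 specifies an adjusted model for hemoglobin decrease that uses the preoperative value only by subtraction. With equal standard deviations, ρ of 0.5 to 0.9 and other covariates ignored, adding it lowers residual variance by 25% down to 5%, narrows the confidence interval by 13% down to 2.5%, and removes the (1 − ρ) share of any chance imbalance. The direction follows from the algebra whenever the true slope differs from 1. The size depends on a correlation that the protocol does not give. The planned test is not invalid, and the primary endpoint is unaffected. The same model's adjustment for staple use, which is observed after randomization and is the primary outcome, is a separate issue and adds no weight here.

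**What to change.** In section 10.1, add preoperative hemoglobin as a continuous covariate in the hemoglobin-decrease regression, and state that the adjusted mean difference between arms will be reported with its 95% confidence interval. Either the decrease or the day-1 value may serve as the outcome, since the treatment comparison is the same.

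The next sentence of section 10.1 carries the same analyses over to re-interventions, so the addition should be worded to apply to the hemoglobin model only.

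The cost is one line of text and one degree of freedom. No data are added, and no patient is lost through the new covariate: anyone without a preoperative value has no computable decrease either.

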## **8. METHODS**

### **8.1 Study parameters/endpoints**

#### **8.1.1 Main study parameter/endpoint**

Primary outcome measure is peroperative use of hemostatic staples.

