### **10.2 Secondary study parameter(s)**

Differences in rates of DVT (yes/no), PE (yes/no) and in rates of administration of postoperative tranexamic acid (yes/no) between the 2 groups will be calculated using Chi-Square (Fisher's Exact) tests.

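### Section 10.1 adjusts the haemoglobin and re-intervention analyses for post-treatment variables, so they do not estimate the total effect that the secondary objective asks about

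*Protocol*

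**What the plan says.** Section 10.1 states for haemoglobin: "The difference in hemoglobin decrease will be tested using multivariate linear regression analysis", "correcting for comorbidities (hypertension, diabetes, dyslipidemia) and use of hemostatic staples". It goes on: "These same analyses will be performed to assess the differences in amount of patients needing to undergo a re" (the word re-intervention breaks across a line here), with one change, "adding administration of postoperative tranexamic acid as a covariate".

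Elsewhere the protocol treats the same two variables as results of treatment:

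- Section 8.1.1: "Primary outcome measure is peroperative use of hemostatic staples".
- Section 4.4 bases the sample size on an "expected 50% decrease of the percentage of patients for whom placement of hemostatic staples was required peroperatively".
- Section 5.1 places the study infusion at induction, so staple use follows it.
- Section 10.2 tests the difference "in rates of administration of postoperative tranexamic acid (yes/no) between the 2 groups".

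The secondary objective in section 2 asks whether giving tranexamic acid (TA) leads to a smaller haemoglobin fall and fewer reoperations for haemorrhage. The protocol gives no version of either analysis without the post-treatment covariates, and it does not describe the adjusted models as mediation or sensitivity analyses.

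**The concern.** A covariate that treatment can change is not a baseline confounder. Comparing arms at equal staple use asks a different question from the one in section 2: what TA does to haemoglobin apart from any effect that runs through staple use. Randomisation does not protect that comparison. It balances the arms as a whole, but not among patients who needed staples or among those who did not. If TA halves staple use, the treated patients who still need staples are likely to be a more bleeding-prone group than the controls who need them.

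Haemoglobin decrease is the first-listed secondary outcome and the only continuous one. With very few haemorrhages expected, it carries most of the secondary evidence on blood loss. A trial that succeeds on its primary outcome could report too small, too large or even a wrongly signed haemoglobin effect, simply because of the covariate list.

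**Working it through.** **Inputs from the protocol.** Clip rate at the centre 63.3% (section 1); expected relative reduction 50% (section 4.4), so 63.3% / 2 = 31.65% under TA; two-sided 5%, 80% power, 2 x 36 = 72 patients (section 4.4); planned inclusion 100 patients, equal allocation (section 3); haemorrhage rate after sleeve gastrectomy at the centre 2.2% (section 1). The protocol uses clips and staples for the same outcome, and they are read as one here.

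**Does the design shift match the plan's own figure?** Unpooled two-proportion formula:

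n per arm = (1.960 + 0.842)² x [0.633 x 0.367 + 0.3165 x 0.6835] / (0.633 - 0.3165)² = 35.15, so 36 per arm and 72 in total.

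This reproduces section 4.4. The plan therefore assumes that treatment moves the covariate by 63.3 - 31.65 = 31.65 percentage points.

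**What adjustment does.** Let Y be the haemoglobin fall, so a negative treatment effect is a benefit. Let b be the staple coefficient in the adjusted model. In linear regression on treatment and staple use:

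adjusted effect = total effect + 0.3165 x b.

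The baseline comorbidities are balanced by randomisation and do not change this in large samples. The two effects agree only if b = 0. The sign of b sets the direction of the shift:

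- b is positive if staple use mainly marks bleeding.
- b is negative if placing a staple or clip mainly limits blood loss.
- b also absorbs any unmeasured bleeding tendency that affects both staple use and haemoglobin.

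**Illustration.** The haemoglobin coefficients are assumptions, with residual SD 1. Here d is the direct effect of TA, g the effect of staple use on the fall, and u the effect of an unmeasured bleeding tendency that accounts for 30% of the variance of the latent variable behind staple use. Total effect = d - 0.3165 x g. Results are from a simulation of 1,000,000 patients.

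| d | g | u | Total | Staple-adjusted |
|---|---|---|---|---|
| 0 | 0.5 | 0 | -0.159 | -0.002 |
| -0.2 | 0.5 | 0 | -0.362 | -0.204 |
| -0.2 | 0.5 | 0.3 | -0.360 | -0.116 |
| -0.2 | 0 | 0.3 | -0.202 | -0.117 |
| -0.2 | -0.3 | 0 | -0.110 | -0.204 |
| -0.2 | -0.3 | 0.3 | -0.104 | -0.114 |
| 0 | 0 | 0.3 | 0.001 | 0.086 |

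Hand check, row 1: 0.3165 x 0.5 = 0.158, and the simulated shift is -0.002 + 0.159 = 0.157. Row 5: 0.3165 x (-0.3) = -0.095, and the simulated shift is -0.204 + 0.110 = -0.094.

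So adjustment removes the effect in row 1, removes (0.362 - 0.204) / 0.362 = 44% of it in row 2, nearly doubles it in row 5, and creates apparent harm from nothing in row 7.

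**Re-intervention.** Expected haemorrhages: 0.022 x 100 = 2.2 in all, or 0.022 x 50 = 1.1 per arm if TA has no effect. Under the definition in section 8.1.2, re-intervention is only one part of haemorrhage. The model as written would carry treatment, three comorbidities, staple use and postoperative TA on about two events.

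**The case against.** Several limits are fair and stand.

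- **The outcomes are secondary.** Section 10.1 is headed as primary, so a reader might infer that the primary analysis is compromised. It is not: staple use is compared by an unadjusted chi-square test, and the sample size rests on that comparison alone. The data for a correct haemoglobin analysis are collected anyway.
- **Adjustment need not shrink the effect.** A reader might infer that the models always adjust the benefit away, or might quote one percentage loss. The documents do not support this. Complete removal needs the whole effect to run through staple-requiring bleeding. A clip or staple is also a haemostatic measure, and then adjustment can enlarge the effect.
- **The reason for postoperative TA is not stated.** A reader might infer that it is given here for suspected bleeding. Sections 1 and 6.3 say so only of a cited study; for this trial, section 8.3 merely has it recorded and section 5.3 lists no escape medication. The narrower argument is enough: it is given after the study treatment, and section 10.2 compares it between arms.
- **The link to re-intervention is loose.** The sentence that carries the analyses over follows both the chi-square and the regression sentence, so an unadjusted comparison may be intended too. Carrying over staple use is the natural reading, not a certain one. The added postoperative TA covariate is explicit.

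A statistical analysis plan that is not at hand does not answer the point, because the protocol itself fixes these covariates.

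**Conclusion.** The point holds for the secondary analyses. The haemoglobin model conditions on the primary outcome, and the re-intervention analysis adds a second post-treatment variable that is itself an outcome in section 10.2. Neither coefficient estimates the total effect in section 2. Each is a direct effect, valid even as such only if nothing unmeasured drives both the covariate and the outcome.

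Neither the direction nor the size can be settled from the protocol, which gives no haemoglobin effect, no SD and no split between direct and mediated effect. Only the 31.65-point shift comes from the plan; every haemoglobin figure above rests on assumed coefficients and an assumed causal structure. For re-intervention the practical loss is small, since about two events cannot inform a multi-covariate model in any case. Haemoglobin is where the correction matters.

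**What to change.** In section 10.1:

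1. Delete staple use from the haemoglobin model. Keep only covariates measured before the study infusion: the three comorbidities and, if wanted, preoperative haemoglobin. The boundary should be the infusion rather than randomisation, because patients are randomised after consent at the outpatient clinic (section 8.2) while the haemoglobin sample is drawn in the week before surgery (section 8.3) and may follow randomisation.
2. Delete staple use and postoperative TA from the re-intervention analysis, and compare the arms with Fisher's exact test, as section 10.2 already does for other rare events. Postoperative TA stays as a between-arm comparison in section 10.2.
3. If the mechanism is of interest, label any staple-adjusted model exploratory and state that it does not estimate the total effect.

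The cost is a few sentences of text. No further data are needed and the sample size does not change. The change should be made before outcomes are analysed by arm.
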